8.3.1 Split Treatment

In the event that a subject is enrolled late in the day on Day 1 and does not complete the first treatment by 1700 hours such that the second treatment on Day 1 cannot be completed by 2300 hours, the subject's first treatment will be on Day 1 PM and the second treatment and televisit will

	Page 41 of 70
EmitBio Inc.	Version: 3.1
EB-P30-01	7 February 2024

occur on Day 2 AM. Thereafter, am/morning and pm/evening treatments will continue until the 14th treatment with the final treatment on Day 8.

The 14th treatment on Day 8 may or may not occur in the clinic depending on the scheduling of the Day 8 follow up visit. The site clinical staff must determine whether the Day 8 treatment will be in clinic or via televisit and convey to the DCT staff. The DCT staff cannot make decisions on treatment or clinic visits; they are only responsible for televisits and televisit scheduling.

A split schedule will occur as follows:

Treatment 1	Day 1 PM	Treatment Diary Only
		In RMP:
		-COVID-19 Symptom Assessment
		-Temperature and Oxygen
		-Antigen Test
		-Treatment Administration
Treatment 2 Diary	Day 2 AM	COVID-19 Symptom Assessment
rioutinont 2 Diary	Duj 2 1111	Temperature and Oxygen
		Antigen Test
		Treatment Administration
Treatment 3 Diary	Day 2 PM	COVID-19 Symptom Assessment
i i outinoite 5 Diary	Duj 21111	Temperature and Oxygen
		Antigen Test
		Treatment Administration
Treatment 4 Diary	Day 3 AM	COVID-19 Symptom Assessment
Troutinent + Diary	Duf 5 min	Temperature and Oxygen
		Antigen Test
		Treatment Administration
Treatment 5 Diary	Day 3 PM	COVID-19 Symptom Assessment
Treatment 5 Diary	Duy 51 W	Temperature and Oxygen
		Antigen Test
		Treatment Administration
Treatment 6 Diary	Day 4 AM	COVID-19 Symptom Assessment
i i outinone o Diary	Duj Thii	Temperature and Oxygen
		Antigen Test
		Treatment Administration
Treatment 7 Diary	Day 4 PM	COVID-19 Symptom Assessment
Troutinent / Drury	Duj TIM	Temperature and Oxygen
		Antigen Test
		Treatment Administration
Treatment 8 Diary	Day 5 AM	COVID-19 Symptom Assessment
		Temperature and Oxygen
		Antigen Test
		Treatment Administration
Treatment 9 Diarv	Dav 5 PM	COVID-19 Symptom Assessment
5	5	Temperature and Oxygen
		Antigen Tes
		Treatment Administration
Treatment 10 Diary	Day 6 AM	COVID-19 Symptom Assessment
5	5	Temperature and Oxygen
		Antigen Test
		Treatment Administration
Treatment 11 Diary	Day 6 PM	COVID-19 Symptom Assessment

		Temperature and Oxygen Antigen Test Treatment Administration
Treature and 12 Diama	Dev 7 AM	COVID 10 Semantary Assessment
Treatment 12 Diary	Day / AM	COVID-19 Symptom Assessment
		Temperature and Oxygen
		Antigen Tes
		Treatment Administration
Treatment 13 Diary	Day 7 PM	COVID-19 Symptom Assessment
		Temperature and Oxygen
		Antigen Test
		Treatment Administration
Treatment 14 Diary	Day 8 AM or PM	COVID-19 Symptom Assessment
		Temperature and Oxygen
		Antigen Test
		Treatment Administration
		Treatment 14 on Day 8 may occur either in the clinic or by
		televisit thereafter all e-Diary entries are completed by the
		study subject without a televisit
Clinic Check	Day 8	
Morning and Afternoon	Days 8 -14	COVID-19 Symptom Assessment
Diaries		Temperature and Oxygen
		Antigen Test
		Return mobile device

8.4 Procedures for Clinically Significant Findings

If in the judgement of the PI any finding poses a previously unknown risk to an individual or leads to a diagnosis of a disease or condition that would have disqualified the individual for enrollment, the study subject will be withdrawn from the study immediately.

All clinically significant findings that occur post randomization and after the first use of the RD-X19 device will be considered TEAEs.

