4.6.2 Exclusion Criteria

A subject with any of the following criteria will be excluded from participation in this study:

- 1. Positive for Influenza A and B antigen using an FDA-authorized rapid diagnostic test.
- 2. Individuals < age 40 on study day 1.
- 3. Individuals who are symptomatic for COVID-19 for more than 72 hours on study day 1.
- 4. COVID-19 signs associated with moderate or greater disease with evidence of lower respiratory involvement including shortness of breath (SOB) at rest or as determined by an exertional SOB protocol, SpO2 ≤94, respiratory rate ≥20 breaths per minute, heart rate ≥90 beats per minute, or abnormal pulmonary imaging.
- 5. Any medical disease or condition that, in the opinion of the site Principal Investigator (PI) or appropriate sub-investigator, precludes study participation.
- 6. History of use of a rescue inhaler for uncontrolled asthma within one month of study day 1.
- 7. History of recurrent alcohol intoxication or other recreational drug use (excluding medically prescribed cannabis) within one month of study day 1.
- 8. History of use, within one month of study day 1, of any FDA-authorized treatment for COVID-19. Use of non-approved putative therapies for COVID-19 (hyroxycholorquine, ivermectin, azithromycin) must be discontinued prior to enrollment in the study.
- 9. History of any systemic antiviral therapies within one month of study day 1.
- 10. History of oral or parenteral corticosteroid use within one month of study day 1. Active use of nasal or inhalable steroids is also exclusionary. Topical steroids are not exclusionary.
- 11. History of any chronic medical condition that has required adjustments to the type, dose or schedule of medical treatments within one month of study day 1.
- 12. Requirement to use narcotic medication for analgesia.
- 13. History of vasomotor rhinitis with or without post-nasal drip within one month of study day 1.
- 14. History of hypersensitivity or severe allergic reaction (e.g., anaphylaxis, generalized urticaria, angioedema, other significant reaction) to sun exposure.

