7.5.3 Investigator Decision to Discontinue Subject Use of Device

A subject may be removed from the study for the following reasons post initial device use; however, whenever possible the subject should be followed for safety evaluations per protocol:

• Study non-compliance to protocol requirements that in the opinion of the participating clinical site PI or appropriate sub-investigator poses an increased risk (e.g., missing safety labs) or compromises the validity of the data.

• Lost to follow-up. A subject will be considered lost to follow-up if he or she fails to appear for a follow-up assessment. Extensive effort (i.e., generally three documented contact attempts via telephone calls, e-mail, etc., made on separate occasions) will be made to locate or recall the subject, followed by a couriered delivery of study documents to the subject's home address to determine the subject's health status. These efforts will be documented in the subject's study file.

• Medical disease or condition, or new clinical finding(s) for which continued participation, in the opinion of the participating clinical site PI or appropriate sub-investigator, might compromise the safety of the subject, interfere with the subject's successful completion of this study, or interfere with the evaluation of safety.

• If any TEAE, clinical laboratory abnormality or situation occurs such that continued participation in the study would not be in the best interest of the subject.

- The occurrence of a SAE.
- If the subject is using the device in any manner inconsistent with instructions and protocol directives and procedures.

If the subject agrees, every attempt will be made to follow all TEAEs through resolution or stabilization.

Subjects who withdraw or are lost to follow-up after signing the informed consent form (ICF) and use the RD-X19 device will not be replaced. Subjects who withdraw or are withdrawn from this study after signing the ICF during screening but before randomization will be replaced.

The reason for subject discontinuation or withdrawal from the study will be recorded on the appropriate e-CRF.

Confidential Information; this Protocol is Confidential and Proprietary to EmitBio Inc.

	Page 35 of 70
EmitBio Inc.	Version: 3.1
EB-P30-01	7 February 2024

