7.5.4 Follow-up of Study Subjects Who Discontinue Device Use

Discontinuation of study device use does not constitute discontinuation from the study, and the study procedures should be completed as indicated by the Study Schedule of Activities. If a clinically significant finding is identified, including, but not limited to, changes from baseline (Day 1), after enrollment, the participating clinical trial site PI or qualified designee will determine if any change in subject management is needed. Any new clinically relevant finding will be reported as a TEAE.

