Individuals with a diagnosis of COVID-19 severity greater than mild or, signs and symptoms present for more than 72 hours are not eligible for enrollment.

	Page 39 of 70
EmitBio Inc.	Version: 3.1
EB-P30-01	7 February 2024

Individuals who qualify for inclusion will be immediately randomized for their day 1 visit.

BP, pulse, and respiration should be measured 3 times over an approximate 10 minute period. The average of the 3 measurements constitutes the value to be captured on the e-CRF an EDC. It is important that BP cuffs and sphygnomonometers are adequately sized and calibrated.

An individual may be re-screened if a protocol eligibility criterion, that is not met at the initial time of screening, will be met by rescreening of all assessments within the next 24 hours using the same subject number, provided their number of days since symptom onset remains 72 hours or less.

No individual may be screened more than twice due to a screening failure result as defined above.

Individuals will be provided the results of any screening abnormality necessitating follow-up with their primary care provider.

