 - Subjects will be observed in the clinic for at least 30 minutes post the first RD-X19 illumination. The oropharynx and surrounding tissues will be examined. Reactogenicity assessments will be performed on

Day 1 in the clinic and on days 5, 8, and 14 during clinic evaluations. Interim or unscheduled targeted physical examinations will be performed, if necessary, to evaluate potential TEAEs.

• Vital signs:

Vital sign measurements will include systolic and diastolic BP, HR, breaths per minute, oral temperature and oxygen saturation via a pulse co-oximeter. BP, pulse and respirations and oxygen saturation will be assessed as previously described. Subjects must not eat or drink anything hot or cold within 10 minutes prior to taking their oral temperature or using the RD-X19 device. All subjects will be issued thermometers and small pulse oximeters to measure oral temperature and O₂ saturation on a twice daily basis and record the results on their diary card.

- Urine pregnancy test will be performed locally by the site laboratory at the screening visit. Results will be recorded as study data and referrals made for serological confirmation and follow-up as required.
- e-Diaries: Subjects will be instructed to fill out e-Diaries twice daily to assess their COVID-19 signs and symptoms and record the number of treatments completed. Each of the eight symptoms will be rated on a 4-point scale from none (0) to severe (3). Temperature and oxygen saturation will also be measured and recorded via devices provided by site personnel and taken home by the subject. Televisit contact will be made by with subjects by the decentralized study staff during the home treatments on days 1-7. Observation of use of the device and recording of study data should be timed to coincide with the study subject encounter. Daily contact with study subjects will enhance safety monitoring and reinforce adherence to at-home study procedures.
- COVID-19 Severity Progression
 - There is a risk that subjects with mild COVID-19 may progress to moderate or more severe disease while on study. In such cases, appropriate medical referrals for evaluation and treatment outside of the protocol will be made.
 - Medically attended visits as a result of COVID-19 will be classified into the following categories:
 - 1) those who require medical attention attributed to any severity of COVID-19;

- 2) those who require medical attention attributed to any SAE;

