- 3) Those who progress to moderate disease indicated by new onset shortness of breath (respiratory rate ≥20/minute) and SpO2 of < 96% confirmed by pulmonary imaging or lower airway disease diagnosed by pulmonary imaging involving < 50% of lung parenchyma;

- Those who progress to severe disease with respiratory rate >30/minute and/or O2 saturation ≤93% on room air or lower airway disease confirmed by pulmonary imaging involving ≥ 50% of lung parenchyma;
- 5) Those who require hospitalization for severe COVID-19;
- 6) Those who require endotracheal ventilation or ECMO with or without the use of solumedrol; and
- 7) Those who die.
- Subjects with a primary care, urgent care, or emergency room visit that are not hospitalized as a result of their medical consultation, may continue treatment with the investigational device and should attend regularly scheduled follow up visits per protocol. Subjects that are admitted to the hospital should discontinue all treatment in lieu of standard of care for severe/critical COVID-19 illness or other SAEs. Such subjects' endpoint data will be right censored as specified in the Statistical Analysis Plan (SAP).
 - Subjects who are treated with any FDA-authorized COVID-19 therapy will discontinue treatment but will continue to be followed per protocol. Such subjects' endpoint data will be right censored as specified in SAP.
 - Subjects who first reach clinical resolution on or after study day 11 should be scheduled for their day 14 visit, which has a +/- 2 day window, so that a total of five consecutive visits (including the first resolution visit) are captured where resolution *may* be observed thus allowing the primary clinical sustained resolution endpoint to be met. Under no circumstances, however, may a study subject be scheduled for their day 14 visit beyond study day 16.

	Page 46 of 70
EmitBio Inc.	Version: 3.1
EB-P30-01	7 February 2024

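### Protocol 8.4, read literally, withdraws a subject whose COVID-19 worsens beyond mild, while 8.6, 7.5.4 and the primary endpoint rule expect follow-up; no exception is stated, and the effect is small

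*Protocol*

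**What the plan says.** Protocol 8.4 is a general clause on clinically significant findings. It opens with the PI's judgement, but its consequence is mandatory and applies to the study, not only to the device: a finding that results in any "diagnosis of a disease or condition that would have disqualified the individual for enrollment, the study subject will be withdrawn from the study immediately".

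Two places make COVID-19 beyond mild disqualifying. Exclusion criterion 4 (Protocol 4.6.2) lists "COVID-19 signs associated with moderate or greater disease with evidence of lower respiratory involvement". Protocol 8.1.3 makes ineligible "Individuals with a diagnosis of COVID-19 severity greater than mild", and so uses the word diagnosis for COVID-19 severity.

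Protocol 8.6 has its own heading for progression. It states that "There is a risk that subjects with mild COVID-19 may progress to moderate or more severe disease while on study" and calls for referral to outside care. Subjects with a medical visit who are not hospitalized "may continue treatment with the investigational device and should attend regularly scheduled follow up visits per protocol". Subjects given an authorized COVID-19 therapy "will discontinue treatment but will continue to be followed per protocol". Protocol 7.5.4 adds: "Discontinuation of study device use does not constitute discontinuation from the study". Protocol 7.5.3, which covers new clinical findings among other reasons, is permissive: "A subject may be removed from the study for the following reasons post initial device use".

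Protocol 9.4.1 and SAP 4.1 both keep a subject with disease progression eligible for a later primary event, given five further resolved assessments and no later recurrence or progression.

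**The concern.** A site cannot withdraw a progressor at once and also collect the diary entries that the primary endpoint rule allows for. No text says which section prevails. Because the trial runs at several sites, with none allowed more than 15% of subjects (Protocol 6.2.1), different readings could produce different follow-up for the same event.

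Where 8.4 is applied, the diary stops because the subject got worse. Ordinary censoring treats such a subject as having the same future chance of resolution as those still at risk, which is doubtful for someone who has just progressed. Scheduled safety follow-up would also end for a subject who has deteriorated. Protocol 7.5.3 asks for safety evaluations where possible after removal; 8.4 has no such provision.

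**Working it through.** **1. Who is affected in the primary analysis.** Take a progressor with no qualifying SSSSS sequence and apply the rules in Protocol 9.4.1 and SAP 8.2:
- Hospitalized: censored at 360 h (rule I), whatever 8.4 does.
- Took nirmatrelvir/ritonavir or molnupiravir: censored at first use (rule III), whatever 8.4 does.
- Neither: censored at the last diary entry (rule IV). Under 8.4 that is about the time of progression; under 8.6 it is about Day 14, or there is an event if the subject resolves later.

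Only the third group depends on which section a site follows.

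**2. Other analyses.** The key secondary rule (SAP 8.3.1) and the primary-endpoint sensitivity analysis (SAP 8.2.5) censor subjects who progress to more severe disease at 360 h, with precedence over all other rules. Once progression is recorded, later diary or antigen entries cannot change either result.

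**3. The plan's own figures.** These reproduce and are not in dispute. Events: 163 × 0.90 + 163 × 0.50 = 228.2. Power (Schoenfeld), Φ(√228 × |ln HR| / 2 − 1.96): 95.0% at HR 0.62, 90.2% at 0.65 and 80.0% at 0.69, against a stated 95%, 90% and 80%.

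**4. Size of the effect.** No progression rate is given, so the rates below are assumptions. The check was a simulation with exponential times, 163 per arm, and HR for sham versus RD-X19 (below 1 favours the device, as in the SAP).
- True HR 0.62. Sham median 200 h, between the 170.3 h and 241.2 h of Protocol Table 1. End at 312 h (Day 14).
- Progressors are a random subset, unresolved until exit. Half exit at 72–120 h (Day 5 ± 1) and half at 144–192 h (Day 8 ± 1), since respiratory rate is measured on clinic days (SAP 4.1).
- Every progressor goes to rule IV. If followed instead, either none or half resolve later, at a time uniform from exit + 48 h to 312 h.
- Unstratified Cox model without covariates; 8,000 runs per scenario; Monte Carlo error of each HR about 0.001.

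| Progression, both arms | Subjects of 326 | HR, rule IV | HR, followed, none resolve | HR, followed, half resolve | Shift |
|---|---|---|---|---|---|
| 2% | about 7 | 0.6193 | 0.6253 | 0.6239 | 0.005–0.006 |
| 5% | about 16 | 0.6214 | 0.6358 | 0.6328 | 0.011–0.014 |
| 9% (stress value) | about 29 | 0.6240 | 0.6480 | 0.6443 | 0.020–0.024 |

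Early withdrawal makes the device look slightly better, because unresolved progressors leave the risk set instead of diluting the contrast. At 5%, power is 94.8% under rule IV, against 92.8% (none resolve) or 94.2% (half resolve) when followed.

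If only half of progressors are withdrawn, the 5% shift is 0.006–0.007. Other inputs (earlier or later exits, sham median 170.3 h or 241.2 h, end at 360 h) put the 5% shift between 0.011 and 0.019.

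With no treatment effect (20,000 runs), one-sided error under rule IV is 2.59% at 5% progression and 2.51% at 9%, against 2.50–2.62% when followed. The Monte Carlo standard error is √(0.025 × 0.975 / 20,000) = 0.11 percentage points, so there is no sign of inflation.

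One limit of the model: before progressors are removed it expects 163 × (1 − 2^(−312/200)) + 163 × (1 − 2^(−312/(200 × 0.62))) = about 242 events, more than the planned 228. Its power figures are therefore slightly optimistic; the comparison between the two handlings is the useful part.

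**The case against.** The strongest reply is that 8.4 is a general safety clause that never mentions COVID-19 and leaves the finding to the PI's judgement, while worsening of the study disease has its own headed procedure in 8.6. The specific text would normally govern, and Protocol 4.3, 8.1.3 and 9.4.1 all point towards follow-up. This stands as far as it goes: follow-up is the more natural reading. It does not remove the problem, because the judgement attaches to the finding while the consequence is fixed, and nothing in 8.4 excludes the study disease.

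A reader might take SAP 7.2, which lists progression as a reason for not completing the study, as proof that progressors are meant to leave. It does not show that. The same list contains screen failure and pregnancy, although it concerns randomized subjects and pregnant women are eligible (Protocol 4.6.1 and 8.8). It looks like a generic exit-form menu.

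It is also fair to say that the affected group is smaller than the one simulated, since rules I and III take some progressors. The simulated shifts are therefore an upper case at each assumed rate.

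**Conclusion.** The conflict in the text is real, and its statistical consequence is small. Under equal progression rates of 2% to 5%, with all progressors withdrawn, the primary HR moves by about 0.005 to 0.014 in the device's favour, without type 1 error inflation. This rests on assumed rates, random progression and the simple exponential model above. The case for repair is that outcome-dependent censoring and lost safety follow-up can be avoided at almost no cost.

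Three stronger conclusions might be drawn, and the documents do not support them.
- That the key secondary result is damaged by missing antigen tests: recorded progressors are already placed at 360 h.
- That the pivotal result could be seriously distorted: a wider shift, −0.010 to +0.032, appears only if progression differs by arm (2% versus 5%), for which the documents give no basis.
- That the earlier 31-subject trial bounds the rate: Protocol 4.1 reports no medical intervention beyond over-the-counter self-medication. An exact one-sided 95% upper limit for 0/31 is 1 − 0.05^(1/31) = 9.2%, but that counts interventions at a different dose, not progression in this population.

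**What to change.** In Protocol 8.4, replace the immediate-withdrawal clause with wording such as: *discontinued from device use and followed per Section 7.5.4, subject to Section 7.5.3; progression of COVID-19 is handled under Section 8.6, with e-diary and visits continuing to Day 14 where feasible for subjects not hospitalized*.

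This keeps the investigator's power under 7.5.3 to remove a subject, leaves hospitalized subjects to their existing tracking and censoring, and leaves device use after progression to 8.6 as written. No change to the primary analysis is needed.

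The cost is about one sentence, since the diary and visits already exist. The downside is that sites must keep contact with a few subjects under outside care, some of whom may still leave.

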8.5 Bio-specimen Collection

A single nasopharyngeal swab and sample will be collected at the baseline (Day 1) visit to assess quantitative viral load and for genetic sequencing in a subset of samples.

Twice daily swabs of the nares will be taken by study subjects to assess the presence or absence of SARS-CoV-2 antigen. This is a FDA-authorized home diagnostic test that involves little to no discomfort and takes approximately 15-20 minutes to complete.

8.6 Safety and Other Assessments

Study procedures are specified in protocol Section 4.6, Schedule of Activities. A study clinician, licensed to make medical diagnoses as the participating clinical site PI or appropriate sub-investigator, will be responsible for all study-related medical decisions.

• Medical history:

	Page 43 of 70
EmitBio Inc.	Version: 3.1
EB-P30-01	7 February 2024

- A complete medical history will be obtained by interview of subjects at the screening visit. Subjects will be queried regarding a history of significant medical disorders of the head, ears, eyes, nose, throat, mouth, cardiovascular system, lungs, gastrointestinal tract, liver, pancreas, kidney, urologic system, nervous system, blood, lymph nodes, endocrine system, musculoskeletal system, skin, and genital/reproductive tract. A history of any allergies, cancer, immunodeficiency, psychiatric illness, substance abuse, and autoimmune disease will be solicited.
- At all subsequent visits, an interim medical history will be obtained by interview of subjects and any changes since the previous clinic visit will be noted. The interim medical history should include an assessment for new medical conditions and symptoms starting since initiating treatment that are suggestive of a TEAE.
- Physical examination:
 - A full physical examination will be performed at the screening visit and on study day 14, and a symptom-directed (targeted) physical examination will be performed if indicated on study days 5 and 8 or at any time an unscheduled visit is required.
 - A full physical examination will include assessments of the following organs and organ systems: skin, HEENT, neck, lungs, heart, liver, spleen, abdomen, extremities, lymph nodes (axillary and cervical), and nervous system.
 - Height and weight will be measured, and BMI calculated, at the screening visit only.
 - A symptom-directed (targeted) physical examination will be performed if indicated during other scheduled clinical site visits.
 - Targeted physical examinations will primarily focus on assessment of signs and symptoms starting since initiating treatment that are suggestive of TEAEs and an examination of the oropharynx. Interim or unscheduled physical examinations will be performed at the discretion of the participating clinical site PI or appropriate sub-investigator, if necessary, to evaluate TEAEs.
 - Subjects will be observed in the clinic for at least 30 minutes post the first RD-X19 illumination. The oropharynx and surrounding tissues will be examined. Reactogenicity assessments will be performed on

Day 1 in the clinic and on days 5, 8, and 14 during clinic evaluations. Interim or unscheduled targeted physical examinations will be performed, if necessary, to evaluate potential TEAEs.

• Vital signs:

Vital sign measurements will include systolic and diastolic BP, HR, breaths per minute, oral temperature and oxygen saturation via a pulse co-oximeter. BP, pulse and respirations and oxygen saturation will be assessed as previously described. Subjects must not eat or drink anything hot or cold within 10 minutes prior to taking their oral temperature or using the RD-X19 device. All subjects will be issued thermometers and small pulse oximeters to measure oral temperature and O₂ saturation on a twice daily basis and record the results on their diary card.

- Urine pregnancy test will be performed locally by the site laboratory at the screening visit. Results will be recorded as study data and referrals made for serological confirmation and follow-up as required.
- e-Diaries: Subjects will be instructed to fill out e-Diaries twice daily to assess their COVID-19 signs and symptoms and record the number of treatments completed. Each of the eight symptoms will be rated on a 4-point scale from none (0) to severe (3). Temperature and oxygen saturation will also be measured and recorded via devices provided by site personnel and taken home by the subject. Televisit contact will be made by with subjects by the decentralized study staff during the home treatments on days 1-7. Observation of use of the device and recording of study data should be timed to coincide with the study subject encounter. Daily contact with study subjects will enhance safety monitoring and reinforce adherence to at-home study procedures.
- COVID-19 Severity Progression
 - There is a risk that subjects with mild COVID-19 may progress to moderate or more severe disease while on study. In such cases, appropriate medical referrals for evaluation and treatment outside of the protocol will be made.
 - Medically attended visits as a result of COVID-19 will be classified into the following categories:
 - 1) those who require medical attention attributed to any severity of COVID-19;

- 2) those who require medical attention attributed to any SAE;
- 3) Those who progress to moderate disease indicated by new onset shortness of breath (respiratory rate ≥20/minute) and SpO2 of < 96% confirmed by pulmonary imaging or lower airway disease diagnosed by pulmonary imaging involving < 50% of lung parenchyma;

- Those who progress to severe disease with respiratory rate >30/minute and/or O2 saturation ≤93% on room air or lower airway disease confirmed by pulmonary imaging involving ≥ 50% of lung parenchyma;
- 5) Those who require hospitalization for severe COVID-19;
- 6) Those who require endotracheal ventilation or ECMO with or without the use of solumedrol; and
- 7) Those who die.
- Subjects with a primary care, urgent care, or emergency room visit that are not hospitalized as a result of their medical consultation, may continue treatment with the investigational device and should attend regularly scheduled follow up visits per protocol. Subjects that are admitted to the hospital should discontinue all treatment in lieu of standard of care for severe/critical COVID-19 illness or other SAEs. Such subjects' endpoint data will be right censored as specified in the Statistical Analysis Plan (SAP).
 - Subjects who are treated with any FDA-authorized COVID-19 therapy will discontinue treatment but will continue to be followed per protocol. Such subjects' endpoint data will be right censored as specified in SAP.
 - Subjects who first reach clinical resolution on or after study day 11 should be scheduled for their day 14 visit, which has a +/- 2 day window, so that a total of five consecutive visits (including the first resolution visit) are captured where resolution *may* be observed thus allowing the primary clinical sustained resolution endpoint to be met. Under no circumstances, however, may a study subject be scheduled for their day 14 visit beyond study day 16.

	Page 46 of 70
EmitBio Inc.	Version: 3.1
EB-P30-01	7 February 2024

